### 6.2 DETAILS OF TRIAL PROCEDURES AT SELECTED VISITS

Trial procedures to be performed at each visit are listed in the Flow Chart and the respective protocol sections. Explanations of procedures are provided in [section 5](#). Additional details regarding visit procedures are provided below. Please also reference the RDC instructions provided in the ISF for clarification on eCRF issues.

Sample collection for C-peptide at screening (Visit 1) and all other visits must be performed in fasted state (at least 10 hours with nothing to eat or drink except water).

At the end of every visit from Visit 2 to 8 the patient must be reminded to bring HBGM log, and the dispensed medication kit (from Visit 3) at the next scheduled visit. Preferably, a phone call to remind the patient must take place one or two days before the patient's next visit.

## 6.2.1 Screening and run-in period(s)

### Screening Period

No trial procedures should be done unless the patient has consented to taking part in the trial. Once they have consented, the patient is considered to be enrolled in the trial and should then be recorded in the enrolment log, and screening will be started. The patient should be registered in the IRT and recorded in the eCRF as a screened patient at Visit 1.

Sample collection for C-peptide should be in fasted state, other procedures at the visit can be in fed condition. If the patient comes for screening visit in fed state, all the procedures can be performed that day and those for fasting is conducted as soon as possible within the screen window. Hence all the procedures for Visit 1 may be performed at different days.

All patients on Visit 1 do not proceed to the next visit until laboratory results are reviewed by investigator.

Details of any patient who is screened for the study but is found to be ineligible must be entered in an enrolment log, registered as a screen failure in the IRT (refer to IRT user manual) and documented in the eCRF.

### Run-in Period

From this visit on, patients should be fasting (no food or drinks, water only for at least 10 hours) prior to each visit.

Patients who fail the run-in period following Visit 2 procedures should be registered as a screen failure in the IRT (refer to IRT user manual).

For background treatment details please see [section 4.2.1](#)

Monitor adverse events, document in the patients' file (source data) and eCRF.

Instruct patients on the correct use of HBGM for glucose testing during the 2 week Run-In Period

- Patients should use the HBGM equipment/supplies to test glucose levels in a fasting state. During the Run-in period patients should test once a day before breakfast (i.e. after an overnight fast). Additionally, patients should test their glucose levels if they experience signs/symptoms of hypo- or hyperglycemia. Test results should be documented on the HBGM testing log. More frequent HBGM testing is permitted at the Investigator's and/or patient's discretion.
- If the HBGM test reveals an overnight fasted blood glucose of  $>240$  mg/dl ( $>13.3$  mmol/l), the patient should contact the study site for a visit at the next day. The investigator will then draw a new blood sample (overnight fasted samples for FPG determination) to confirm the hyperglycemia, document the AE if appropriate and decide about the possible exclusion from randomisation (screening failure).

The subject will be instructed to perform an 8-point HBGM over a single 24-hour time period (approximately) within one week prior to Visit 3. The plasma glucose levels should be measured and recorded in the log (including date, time and value) at the defined time points, details please see [section 5.1](#).

### Baseline Conditions

Chronic diseases, current observable conditions, any new clinically relevant findings discovered from the physical examination, ECG, safety labs, and any condition requiring therapy (excluding T2DM) will be reported on the Baseline Condition eCRF page.

**Medical History:**

Medical history will be collected and reported in the Medical History eCRF page. Information on clinically significant previous and concomitant illnesses, other than T2DM, or any clinically significant signs or symptoms that are present before informed consent, or pre-existing conditions identified through findings from assessments and examinations done during the screening visits will be recorded as medical and surgical history at screening on the Baseline Condition page in the eCRF.

**6.2.2 Treatment period(s)**

Patients must satisfy all inclusion and exclusion criteria prior to randomisation (see [Section 3.3](#)). In addition, if during the placebo run-in period, there is any indication that a patient's conditions of T2DM are not stable enough for the patient to complete the study or that the patient will not be compliant with the study medication or restrictions, the patient should not be randomised to the treatment.

The date of visit should be determined based on the date of Visit 3 and visits should occur within the allowed time frame shown in the [Flow Chart](#).

The treatment period is from Visit 3 to Visit 8/EOT. Patients will be dispensed medication at each of these visits (except for Visit 8/EOT). Medication number of each occasion will be allocated by IRT (refer to IRT user manual).

Patients should not take study medication at home on the morning of trial visits during the treatment period.

**Randomisation visit (Visit 3)**

Visits should be performed fasting and as indicated in the Flow Chart and the respective protocol sections.

- Collection of urine and blood for laboratory testing must be performed prior to administration of study medication
- ECG is performed and evaluated
- Blood pressure should always be measured before taking any blood sample, details see [Appendix 10.1](#)
- Collect returned run-in medication
- Collect the HBGM test log
- Contact IRT to randomize patient and obtain medication kit numbers and dispense the medication to the patient
- After the patient has finished breakfast and last blood sample collected as MTT, administer first dose of study medication, which should be the last activity at this visit
- Patients should be reminded about the importance to follow the agreed diet and exercise plan
- Instruct patient NOT to take study medication and background medications on the morning of trial visits as described in [Section 4.1.4](#)

**Visits 4-8/EOT**

Visits should be performed as mentioned in the Flow Chart and the respective protocol sections.

- Collection of urine and blood for laboratory testing must be performed prior to

Proprietary confidential information © 2021 Boehringer Ingelheim International GmbH or one or more of its affiliated companies

administration of study medication according to the Flow Chart

- All the patients including the treatment discontinued should perform the MTT and follow the process described in [Section 5.1](#)
- Blood pressure should always be measured before taking any blood sample, details see Appendix 10.1
- Collect returned medication prior to dispensing new medication
- Collect the HBGM test log
- New medication kit must be dispensed according to the Flow Chart, and IRT must be contacted at those visits to obtain medication kit numbers to be dispensed
- Patients should be reminded about the importance to follow the agreed diet and exercise plan.
- Instruct patient NOT to take study medication as well as background medications on the morning of trial visits as described in section 4.1.4
- Instruct patients to perform 8-point glucose profile within one week prior to visits as indicated in the Flow Chart
- Visit 8/EOT is the last visit of the treatment period. Study medication will not be dispensed at Visit 8/EOT

If a patient prematurely discontinues from the 24-week treatment period, the patient must return to the trial site for EOT (within 7 days of stopping study treatment) including MTT. The reason for premature trial drug discontinuation must be documented in the eCRF. In addition patients will be encouraged to attend all subsequent planned onsite visits despite not being under treatment anymore and perform all study procedures. If the EOT visit occurs within the time window of a planned visit, the EOT visit will replace the planned visit.

The need for coming to future visits in case of premature discontinuation of trial medication will be explained to patients prior to their participation in the trial.

The investigator may initiate any additional antidiabetic therapy for the patient, based on his or her discretion, no sooner than one day after discontinuing study medication or after Visit 8. Patients who prematurely discontinue the study should be registered as discontinued, and patients who complete the full 24-week double-blind treatment period should be registered as completed in the IRT.

### **6.2.3 Follow-up period and trial completion**

For all patients completing the study according to protocol or prematurely discontinued without persisting AE at Visit 8, a follow-up contact (Visit 9) with the patient (preferably by phone) should be done by the investigator at the end of the followup period of 7 days. The following should be confirmed and recorded at Visit 9:

- Concomitant therapies
- Any AEs
- HBGM result

For patients completing the study according to the protocol or prematurely discontinued from the 24 week treatment period however, agree to return, with persisting AE at Visit 8, the following examinations should be performed at Visit 9 additionally:

- Vital signs
- Collection of blood and urine samples for safety laboratory evaluation
- FPG

**Trial completion**

The trial completion eCRF page has to be filled-in when the patient has terminated the trial.

The end of the trial is:

- At the end of the follow-up visit for patients who have completed the trial on treatment as planned;
- After the early end of treatment (EOT) and follow-up visits, if a patient did not agree to come to the remaining planned study visits;
- At the end of Visit 9 for patients who discontinued drug early but agreed to come to the remaining planned study visits.

## **7. STATISTICAL METHODS AND DETERMINATION OF SAMPLE SIZE**

### **7.1 NULL AND ALTERNATIVE HYPOTHESES**

The superiority of Empagliflozin (10 mg q.d. and 25 mg q.d.) over placebo will be tested using the hierarchical hypothesis testing procedure. The following two sets of hypotheses will be tested sequentially each at the level of  $\alpha = 0.05$  (two-sided). The second null hypothesis ( $H_{0,2}$ ) for Empagliflozin 10 mg vs. placebo will be tested confirmatively only if the first null hypothesis ( $H_{0,1}$ ) for Empagliflozin 25 mg vs. placebo is rejected. If the first null hypothesis ( $H_{0,1}$ ) is not rejected, the second null hypothesis ( $H_{0,2}$ ) will be tested in an exploratory fashion.

Step 1: The superiority of empagliflozin 25 mg against placebo will be tested for change from baseline in HbA1c after 24 weeks of treatment at the level of  $\alpha=0.05$  (two-sided).

$H_{0,1}$ : Mean change from baseline in HbA1c after 24 weeks of treatment with Empagliflozin (25 mg q.d.) = Mean change from baseline in HbA1c after 24 weeks of treatment with placebo

$H_{1,1}$ : Mean change from baseline in HbA1c after 24 weeks of treatment with Empagliflozin (25 mg q.d.)  $\neq$  Mean change from baseline in HbA1c after 24 weeks of treatment with placebo

Step 2: The superiority of empagliflozin 10 mg against placebo will be tested for change from baseline in HbA1c after 24 weeks of treatment at the level of  $\alpha=0.05$  (two-sided).

$H_{0,2}$ : Mean change from baseline in HbA1c after 24 weeks of treatment with Empagliflozin (10 mg q.d.) = Mean change from baseline in HbA1c after 24 weeks of treatment with placebo

$H_{1,2}$ : Mean change from baseline in HbA1c after 24 weeks of treatment with Empagliflozin (10 mg q.d.)  $\neq$  Mean change from baseline in HbA1c after 24 weeks of treatment with placebo

### **7.2 PLANNED ANALYSES**

#### **7.2.1 General considerations**

The statistical analyses will be performed on the following population.

##### **Treated set (TS)**

The TS will consist of all patients who are randomized and treated with at least one dose of the study drug. The assignment of patients to treatment groups will be based on the actual first study drug intake in the double-blind treatment period.

##### **Modified Intention-to-Treat (mITT) set**

The mITT set will consist of all randomized patients who are treated with at least one dose of the study drug and have a baseline HbA1c assessment. The assignment of patients to treatment groups will be based on the planned randomised study drug at the time of randomisation.

### **Per Protocol set (PPS)**

The PPS will consist of all patients in mITT set who do not have important protocol deviation (iPD) that may have a distorting influence on the assessment of the primary endpoint. The definitions of iPDs and the details of the handling of iPDs will be provided in the trial statistical analysis plan (TSAP).

With regard to efficacy and safety endpoints, the term “baseline” refers to the last observed measurement prior to administration of any randomised study drug.

#### **7.2.2 Primary endpoint analyses**

The primary endpoint in this trial is the change in HbA1c (in unit of %) from baseline after 24 weeks of treatment. The baseline HbA1c refers to the last HbA1c assessment prior to the administration of any randomized study drug and not to the HbA1c assessment used for the stratification in the randomisation.

##### **7.2.2.1 Primary analysis of the primary endpoint**

The primary analysis is a restricted maximum likelihood (REML) based approach using a mixed model for repeated measures (MMRM) comparing the mean change in HbA1c from baseline after 24 weeks of treatment. The analysis will include treatment (Empagliflozin 10 mg, Empagliflozin 25 mg, placebo), background therapy (insulin only, insulin with OAD), and visit as fixed classification effects, baseline HbA1c and baseline eGFR as the linear covariates, treatment by visit interaction, and baseline HbA1c by visit interaction.

The statistical model will be as follows.

HbA1c change from baseline at each on-treatment visit = overall mean

+ treatment + background therapy  
+ baseline HbA1c + baseline eGFR  
+ visit + treatment-by-visit interaction  
+ baseline HbA1c-by-visit interaction  
+ random error

Visit will be treated as the repeated measure with an unstructured covariance structure used to model the within-patient measurement.

The Kenward-Roger approximation will be used to estimate the denominator degrees of freedom and adjust standard errors. Significance tests will be based on least-squares means using a two-sided  $\alpha=0.05$  (two-sided 95% confidence intervals). The residuals are assumed to

Proprietary confidential information © 2021 Boehringer Ingelheim International GmbH or one or more of its affiliated companies

have a multivariate normal distribution with zero means and covariance matrix as specified above. The primary treatment comparisons will be the contrasts between active treatment (Empagliflozin 10 mg and 25 mg, respectively) and placebo at week 24.

The primary analysis will be performed on mITT set with patients assigned to the treatment they are randomised to and include on-treatment HbA1c values only. If a patient misses a visit, the missing data will not be imputed. And all HbA1c values measured after premature discontinuation of study drug or after rescue therapy is initiated will be set to missing. The mixed effect model will handle missing data based on a likelihood method under the "missing at random" assumption.

#### 7.2.2.2 Secondary analyses of the primary endpoint

##### *Sensitivity analysis*

In order to check the sensitivity of the primary analysis results to missing data handling or to premature treatment discontinuation, sensitivity analyses will be performed as follows.

Multiple imputation of HbA1c change from baseline after 24 weeks is planned for on- and off-treatment values for the three treatment groups individually. These analyses will be performed based on all randomised patients who have a baseline HbA1c measurement.

Missing on-treatment values will be imputed using Markov Chain Monte Carlo (MCMC) simulation and standard techniques. Missing off-treatment data will be imputed based on the observed off-treatment data by treatment group, providing at least 6 patients provide off-treatment data at Week 24 in each treatment group. If fewer than 6 patients per treatment group provide off-treatment data at Week 24, on-treatment information from the placebo group will be used as a basis for the imputation. The imputation model will include baseline HbA1c and the last on-treatment value. The analysis model will be an analysis of covariance (ANCOVA) model including treatment, background therapy, and continuous baseline HbA1c and baseline eGFR; a common treatment estimate will be derived based on Rubin's method.

The number of imputations will be set to 100 in order to ensure adequate efficiency and stability of estimation of missing data.

##### *Analysis on further patient set*

The analysis of the primary endpoint will be repeated on the PPS using the same MMRM model as for the primary analysis to assess the impact of important protocol deviations.

##### *Analysis of effectiveness*

The analysis of the primary endpoint will be repeated on the mITT set but include all on- and off-treatment (i.e. measured after premature discontinuation of study drug or after rescue therapy is initiated) HbA1c values using the same MMRM model as for the primary analysis to assess the effectiveness of the study drug.

#### 7.2.2.4 Supplementary analysis

To explore the efficacy of pooled Empagliflozin doses (10 mg q.d. and 25 mg q.d.) over placebo, additional analysis on the primary endpoint will be repeated on the mITT set using the same MMRM model as for the primary analysis. More details will be specified in TSAP.

#### 7.2.3 Secondary endpoint analyses

[figure not shown]
The percentage of patients with  $\text{HbA}_{1c} < 7.0\%$  after 24 weeks of treatment will be summarised in a frequency table by treatment groups and analysed using logistic regression. Odds ratios and their respective 95% confidence intervals and p-values will be obtained.

For continuous secondary endpoints of change from baseline in body weight, SBP, DBP and FPG at week 24, the similar MMRM approach based on on-treatment values for the primary analysis of the primary endpoint will be used. The model will include “baseline value for the corresponding endpoint” and its interaction with visit as additional covariates.

For continuous secondary endpoint of change from baseline in 2-hour PPG at week 24, an ANCOVA model will be applied since PPG is only measured at baseline and week 24. The ANCOVA model will include treatment and background therapy as classification effects, baseline PPG and baseline eGFR as the linear covariates.

Number of patients with hypoglycemic events and DKA events will be tabulated in frequency tables by treatment groups. Logistic regression will be performed to compare the occurrence of hypoglycemic events and DKA events between empagliflorin groups (10 mg and 25 mg, respectively) and placebo. Odds ratios and their respective 95% confidence intervals and p-values will be obtained.

More details of the analysis of secondary endpoints will be specified in TSAP.

## **7.2.5 Safety analyses**

Adverse events will be coded using the Medical Dictionary for Drug Regulatory Activities (MedDRA). Standard BI summary tables and listings will be produced. All adverse events with an onset between start of treatment and end of the REP, a period of 7 days after the last dose of trial medication, will be assigned to the on-treatment period for evaluation.

All treated patients will be included in the safety analysis. In general, safety analyses will be descriptive in nature and will be based on BI standards. No hypothesis testing is planned.

Statistical analysis and reporting of adverse events will concentrate on treatment-emergent adverse events, i.e. all adverse events occurring between start of treatment and end of the REP. Adverse events that start before first drug intake and deteriorate under treatment will also be considered as 'treatment-emergent'.

Frequency, severity, and causal relationship of adverse events will be tabulated by system organ class and preferred term after coding according to the current version of MedDRA at database lock.

Laboratory data will be analysed both quantitatively as well as qualitatively. The latter will be done via comparison of laboratory data to their reference ranges. Values outside the reference range as well as values defined as clinically relevant will be summarised. Treatment groups will be compared descriptively with regard to distribution parameters as well as with regard to frequency and percentage of patients with abnormal values or clinically relevant abnormal values.

Vital signs, physical examinations, or other safety-relevant data observed at screening, baseline, during the course of the trial and at the end-of-trial evaluation will be assessed with regard to possible changes compared to findings before start of treatment.

Further details of the safety analysis will be specified in TSAP.

## **7.2.6 Interim Analyses**

No interim analysis is planned.

### **7.3 HANDLING OF MISSING DATA**

For the analysis of the primary endpoint, the handling of missing data is described in [section 7.2.2.](#)

For percentage of patients with  $\text{HbA}_{1c} < 7.0\%$  after 24 weeks of treatment, the missing data will not be imputed. Patients who prematurely discontinue the treatment or initiate rescue therapy will be treated as non-responder (i.e.,  $\text{HbA}_{1c} \geq 7.0\%$  after 24 weeks of treatment).

No imputation for missing data will be performed for secondary efficacy endpoints of change from baseline in body weight, SBP, DBP and FPG. The missing data will be handled by MMRM model based on a likelihood method under the "missing at random" assumption.

Baseline Observation Carried Forward (BOCF) approach will be used for 2-hour PPG in ANCOVA analysis.

Missing or incomplete AE date will be imputed according to BI standards. Other missing safety data will not be imputed.

### **7.4 RANDOMISATION**

The trial will be performed as a double-blind design with respect to placebo and the two active dose groups of Empagliflozin (10 mg q.d. and 25 mg q.d.). The randomization will be stratified by the following factors:

- $\text{HbA}_{1c}$  value at screening visit (Visit 1) ( $<8.5\%$ ,  $\geq 8.5\%$ )
- Background antidiabetic therapy (insulin alone, insulin + OAD)

Block randomization will be used to randomize patients in a ratio of 1:1:1 to placebo or Empagliflozin 10 mg or Empagliflozin 25 mg.

BI will arrange for the randomisation and the packaging and labelling of trial medication. The randomisation list will be generated using a validated system, which involves a pseudo-random number generator so that the resulting treatment will be both reproducible and non-predictable. The block size will be documented in the Clinical Trial Report. Access to the codes will be controlled and documented.

### **7.5 DETERMINATION OF SAMPLE SIZE**

In the primary MMRM analysis (with excluded off-treatment and post-rescue values), the superiority of empagliflozin 25 mg and the superiority of empagliflozin 10 mg compared to placebo will be tested separately in a hierarchical order at the two-sided alpha level of 0.05.

The effective sample size is calculated from the assumed treatment effect and the assumed covariate-adjusted standard deviation based on a two-sided t-test at alpha-level of 0.05. The effective sample size corresponds to the sample size in the absence of treatment drop-out or censoring, i.e. when all patients complete the 24 week treatment period without prematurely

discontinuing treatment and without initiating rescue therapy. Censored patients still contribute some information to the analysis and are accounted for in the actual sample size. Censored patients are assumed to contribute to sample size according to the amount of information provided as a fraction of a completer. This fraction is referred to as the information content. The sample size (SS) is derived from the effective sample size ( $SS_{eff}$ ), the assumed censoring rate (CR) and the assumed information content (IC) using the following formula:

$$SS = \frac{SS_{eff}}{1 - CR(1 - IC)}$$

Based on the experience in previous studies with Empagliflozin add-on to insulin (e.g. U12-3817-01, U13-2122-01, P19-10212), it is estimated that the difference between Empagliflozin (10 mg q.d., 25 mg q.d.) and placebo in the change in HbA1c from baseline at week 24 is about 0.62% with standard deviation of 1.1%. Given those assumptions, an effective sample size of 68 patients per treatment arm will provide 90% power to detect the standardized effect size of 0.564 (0.62/1.1) based on two-sample t-test at two-sided alpha level of 0.05 for each dose group. Assuming an 8% censoring rate (including premature treatment discontinuation and rescue therapy use) and an information content of 0.4 (based on results from previous studies), 72 patients per treatment arm are needed, leading to a total of 216 patients for three treatment arms.

The sensitivity of the sample size to the different scenarios of the assumptions is shown in Table 7.5: 1. Calculations were performed using nQuery Advisor® 7.0 statistical package by Statistical Solutions Ltd.

Table 7.5: 1 Power estimates for different scenarios for the MMRM analysis at two-sided  $\alpha = 0.05$

Treatment effect (%)	Covariate adjusted standard deviation (%)	Censoring rate	Information content	Effective sample size per treatment arm	Sample size per treatment arm	Power
0.62	1.0	0.08	0.4	68	72	94.8
0.62	1.0	0.15	0.4	66	72	94.2
0.62	1.1	0.08	0.4	68	72	90.3
0.62	1.1	0.15	0.4	66	72	89.5
0.62	1.2	0.08	0.4	68	72	84.8
0.62	1.2	0.15	0.4	66	72	83.7

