7 PLANNED ANALYSES

Disposition of the patient population participating in the trial will be analysed by treatment groups and presented in the clinical trial report as a frequency-distribution. The number of patients participating in the study will also be analysed by treatment group and presented as a frequency distribution.

A frequency of patients with iPDs, also summarised by whether the iPD led to exclusion from the PPS, will be presented by treatment group for treated set. The frequency of patients in different analysis sets will also be presented for each treatment group.

For in-text tables presenting descriptive analysis of the endpoints and other variables (analysed in original scale), the set of summary statistics is: N (number of patients with non-missing values), mean, standard deviation (SD).

For end-of-text tables, the set of summary statistics is: N (number of patients with non-missing values) / Mean / SD / Min / Q1 (lower quartile) / Median / Q3 (upper quartile) / Max.

For the in-text, end-of-text and appendix tables presenting descriptive analysis of the endpoints and other variables (analysed on logarithmic scale), the respective summary statistics (e.g., gMean, gCV, etc.) will be used.

Statistical parameters will be displayed to a defined number of decimal places as specified in the BI guideline "Reporting of Clinical Trials and Project Summaries" (2). Patient level results for the calculated endpoints HOMA-IR will be presented to one decimal place.

HOMA- β will be presented as full integers. The summary statistics of these parameters will follow the aforementioned guideline.

Tabulations of frequencies for categorical data will include all possible categories and will display the number of observations in a category as well as the percentage (%) relative to the respective treatment group. Percentages will be rounded to one decimal place. The category missing will be displayed if and only if there are actual missing values. Percentages will be based on all patients in the respective patient set whether they have non-missing values or not.

In all specified statistical analyses, treatment comparisons will be made between each randomised empagliflozin group (10mg and 25mg) and placebo.

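### The 90% power stated for each dose is not the power of the confirmatory 10 mg test, which is about 84% under the plan's own hierarchy and is not reported

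*Protocol*

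**What the plan says.** Section 7.5 of the protocol opens by saying that superiority of 25 mg and of 10 mg over placebo "will be tested separately in a hierarchical order at the two-sided alpha level of 0.05". The planning difference is given once for both doses, "from baseline at week 24 is about 0.62% with standard deviation of 1.1" (both in HbA1c percentage points). The power statement follows: "an effective sample size of 68 patients per treatment arm will provide 90% power to detect the standardized effect size of 0.564", "based on two-sample t-test at two-sided alpha level of 0.05 for each dose group". Table 7.5:1 then lists six scenarios with one column headed Power; the base case shows 90.3.

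Section 7.1 fixes the order. The second null hypothesis "for Empagliflozin 10 mg vs. placebo will be tested confirmatively only if the first null hypothesis", the one for 25 mg, is rejected. If it is not, the 10 mg hypothesis "will be tested in an exploratory fashion".

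Section 7.4 sets the allocation: "Block randomization will be used to randomize patients in a ratio of 1:1:1 to placebo or Empagliflozin 10 mg or Empagliflozin 25 mg". Both comparisons therefore use the same placebo arm. SAP Section 7 confirms that "treatment comparisons will be made between each randomised empagliflozin group (10mg and 25mg) and placebo", and SAP Section 7.4.1 refers back to the protocol for the testing sequence. Neither document gives a power for the second step or for rejecting both hypotheses.

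**The concern.** Section 7.5 names the hierarchy and then gives one power for both doses as if each test stood alone. That is right for the first test in a fixed sequence. It overstates the second, which yields a confirmatory result only when the first has also succeeded.

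Both doses belong to the confirmatory sequence, so the planned chance of confirming each one is a figure the sample size section should give. A reader who takes 90% as the chance of confirming 10 mg underestimates the risk of missing that claim. The understatement is largest in the less favourable rows of Table 7.5:1, which is where a sensitivity table matters most.

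**Working it through.** **Inputs.** All are from the protocol: difference 0.62 for each dose, SD 1.1, two-sided alpha 0.05, 68 effective patients per arm, censoring rate 0.08 and information content 0.4 (Section 7.5); 1:1:1 allocation (Section 7.4); 25 mg tested before 10 mg (Section 7.1).

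**Step 1: reproduce the plan's figures.** For one comparison the noncentrality is 0.62 / (1.1 × √(2/68)) = 3.287, with 2 × 68 − 2 = 134 degrees of freedom. The noncentral t gives a power of 90.37%, against the stated 90.3%. The inflation is 68 / (1 − 0.08 × (1 − 0.4)) = 68 / 0.952 = 71.4, rounded up to 72 per arm and 216 in total. The other five rows of Table 7.5:1 also reproduce within 0.1 point.

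**Step 2: write down the confirmatory event for 10 mg.** By Section 7.1,

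P(10 mg confirmed) = P(25 mg rejected and 10 mg rejected).

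The two differences share the placebo mean. With equal arms their covariance is σ²/n and each has variance 2σ²/n, so their correlation is 0.5.

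**Step 3: compute the joint power.** As a quick check by normal approximation, each statistic must exceed 1.960 and has mean 3.287, so the margin is 1.327. The bivariate normal probability with correlation 0.5 that both exceed the limit is 84.4%. Simulating three-arm trials with actual t-tests (millions of replicates per row) gives 83.8% with pairwise variances, which is the test named in Section 7.5, and about 84.1% with variance pooled over the three arms. All rows:

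| SD | Effective n per arm | Table 7.5:1 power (%) | Both rejected, pairwise t (%) | Both rejected, pooled variance (%) | Gap, table minus pairwise (points) |
|---|---|---|---|---|---|
| 1.0 | 68 | 94.8 | 91.0 | 91.1 | 3.8 |
| 1.0 | 66 | 94.2 | 90.0 | 90.1 | 4.2 |
| 1.1 | 68 | 90.3 | 83.8 | 84.1 | 6.5 |
| 1.1 | 66 | 89.5 | 82.5 | 82.7 | 7.0 |
| 1.2 | 68 | 84.8 | 75.6 | 75.9 | 9.2 |
| 1.2 | 66 | 83.7 | 74.1 | 74.3 | 9.6 |

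Repeat simulations agree to about 0.1 point.

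**Step 4: split the base case.** The probability that 10 mg is significant while 25 mg is not is 90.37 − 83.83 = 6.5%; in those trials 10 mg would be exploratory only. Given that 25 mg is rejected, the power for 10 mg is 83.83 / 90.37 = 92.8%.

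**Step 5: scale.** At SD 1.1, 80 effective patients per arm is the smallest number that gives at least 90% joint power with t-tests (about 90.1%; 79 gives 89.7%). The plan's inflation turns this into 80 / 0.952 = 84.03, so 85 per arm and 255 in total. The normal approximation would give 79 effective and 83 per arm. These numbers only show the size of the gap; no increase is proposed.

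**The case against.** The strongest reply is that no printed number is wrong. Section 7.5 names its basis, a two-sample t-test for each dose, and as a marginal power the statement is true. The hierarchy is disclosed in the same section and in Section 7.1, no joint-power target is set anywhere, and sizing a trial on the marginal power of each comparison with the first-ranked dose fully powered is a legitimate choice. In the 6.5% of trials at issue the 10 mg data are still analysed; what is lost is confirmatory status. The SD 1.2 rows are pessimistic scenarios for which the protocol already reports lower power, and at SD 1.0 the joint power remains 90% to 91%.

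Most of this stands. It means that this is a gap in how power is described, not a calculation error, and that the sample size need not change. It does not rescue the wording. A marginal power applied to each dose group, directly after the hierarchy is introduced, invites the reading that the confirmatory 10 mg test has 90% power. Under Section 7.1 it does not, and no other passage supplies the right figure.

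One might also object that the correlation is assumed. It follows from equal allocation and the shared placebo arm. Treating the two tests as independent would give 0.9037² = 81.7%, further from 90%.

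**Conclusion.** The concern holds. For 25 mg, 90% is the correct confirmatory power. For 10 mg it is about 84% in the planning scenario, a shortfall of about 6.5 points, with a range from about 74% to 91% across the rows of Table 7.5:1.

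These figures take the protocol's planning assumptions at face value: the same 0.62 effect for both doses, a common SD, and the effective sample size treated as complete data in every arm. If the true effect of either dose is smaller than 0.62, the joint power is lower. Type I error control, the hypotheses and the planned analyses are not affected. The point should be corrected, but it does not question the design.

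**What to change.** Keep 216 patients. In Section 7.5, replace the single power statement with two: 90% power for 25 mg versus placebo, and about 84% power for the confirmatory test of 10 mg versus placebo, defined as rejection of both null hypotheses under the assumption of equal effects. In Table 7.5:1, label the present power column as power for a single comparison and add a column for power to reject both null hypotheses. In row order the pairwise t values are 91.0, 90.0, 83.8, 82.5, 75.6 and 74.1%. State whether pairwise or pooled variance was used.

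The cost is one sentence, one column label and one table column. One stated figure becomes less favourable. No patients are added, and no test, hypothesis or alpha level changes.
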